5.2. Secondary Endpoints Analysis

Secondary endpoint is defined as immediate operation success rate, which means that left and right disks are effectively fixed on the left and right sides of the atrial septum, respectively, and smoothly released without displacement or migration, and the delivery system is successfully withdrawn.

Secondary endpoints will be summarized descriptively using frequencies and percentages, and no formal statistical inference will be performed. However, the 95% confidence interval for the immediate operation success rate will be calculated using the exact method.

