Device name	Absorbable ASD closure system
Administrative category	Class III medical device
Study design	
(1) Objectives: To evaluate the safety and efficacy of Absnow™ absorbable closure system developed and produced by Lifetech Scientific (Shenzhen) Co., Ltd. for ASD patients;(2) This study is a prospective, multi-center, single-arm OPC clinical trial. It is planned to enroll 146 subjects to implant the closure system, carrying out 9 follow-up visits after the operation and recording the trial process of each subject in detail.(3) Primary safety endpoint: Rate of common complications during 360-day post operation;(4) Primary efficacy endpoint: Effective closure rate at 360-day post operation;(5) The interim report of the clinical trial will be completed after completing the 360-day follow-up post operation and obtaining corresponding clinical data and follow-up data. A registration application will be submitted to NMPA based on the interim report.(6) Before the national multi-center trial is officially launched, a pre-trial with a sample size of five cases (excluding from the overall effective sample size) will be conducted in Guangdong Provincial People's Hospital.
Indications	Patients with secundum ASD
Sample size	146 cases
Number of clinical trial institutions	11
Test time	
(1) First patient in (FPI) date: Aug 2018(2) Subject recruitment time: 6 months

	(3) Completion date of the 360-day follow-up visit of the last subject: March 2020
Efficacy evaluation	(1) Primary efficacy endpoint: effective closure rate at 360-day post operation (effective closure refers to no or only mild-small residual shunt in TTE or TEE observation after device implantation); (2) Secondary efficacy endpoint: immediate operation success rate (immediate operation success means that left and right disks are effectively fixed on left and right sides of atrial septum respectively and smoothly released without displacement or migration, and the delivery system is successfully withdrawn);
Safety evaluation	(1) Primary safety endpoint: Rate of common complications during 360-day post operation (refer to 7.1.7.1 of the main body for details) (2) Others safety endpoints: 
• Rate of device-related AEs;• Rate of SAEs;

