8.9 Subject selection criteria and reasons

- (1) Full analysis set (FAS): According to the basic principles of Intention to Treat (ITT), FAS refers to the set of subjects that comply with the ITT principles. It includes:
- a) Subjects who have been treated with the investigational device, achieved the immediate operation success, and have at least one observation data of primary endpoints after baseline;
 - b) Subjects who have received treatment with the investigational device, but have failed in the implantation because of the device itself, regardless of whether there is test device in the body.

If the implantation is abandoned due to other clinical reasons and there is no investigational device in the body, such subjects will not be included in the FAS. The definition of receiving the investigational device treatment is that if any part of the device, including the occluder itself and its delivery device, contact with human body through vascular approach, it can be considered as receiving the device treatment. FAS will be the main data set for baseline data analysis, primary safety and efficacy evaluation.

- (2) Per protocol set (PPS): refers to subjects who have no serious violation of the study protocol in FAS, have good compliance, have not used drugs or treatments that may affect the efficacy evaluation during the trial, and have no missing data of primary endpoints. Unless otherwise specified, no carrying forward will be performed for the missing data of PPS. Theoretically, PPS should exclude subjects who have not completed all the visit plans due to various reasons, except that whether the subject's ASD has been successfully treated can be judged according to the existing results. PPS will be the secondary data set for efficacy evaluation.
- (3) Safety set (SS): It is used for safety evaluation of the clinical trial, including all subjects who have been treated with the device at least once. SS will be the main data set of safety analysis.
- (4) The efficacy evaluation of the device is mainly based on FAS, and PPS is only used as a reference data set for efficacy evaluation. Safety evaluation is based on SS. According to the above criteria, the subjects will be included in FAS, PPS and SS for interim efficacy evaluation and analysis at 360-day post operation. In the fifth year after operation, the subjects will be also included in FAS, PPS and SS for finally efficacy evaluation

and analysis according to the above criteria.

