4. STATISTICAL CONSIDERATION

For continuous variables, the following will be listed: number of valid cases, mean, standard deviation, median, 25th and 75th percentiles, minimum value, and maximum value. The number of decimal places for the 25th and 75th percentiles, minimum, and maximum values will match the records in the database. The mean and median will retain one more decimal place than the raw data recorded in the database, while the standard deviation will retain two more decimal places than the raw data recorded in the database.

For categorical variables, data will be presented in frequency tables (frequencies and percentages). Percentages will be rounded to one decimal place. When the frequency is zero, only the frequency needs to be listed; the percentage may be omitted to distinguish it from non-

zero values. When calculating percentages, the number of subjects in the specified analysis population will serve as the denominator.

All hypothesis tests employ one-sided tests unless otherwise specified, with a statistical significance level of $\alpha=0.025$. Differences are considered statistically significant when $P<0.025$. All confidence intervals were calculated at the 95% confidence level. P-values were rounded to three decimal places. If $P < 0.001$, the value was output as “<0.001”. If $P > 0.999$, the value was output as “>0.999”.

All analyses in the safety evaluation are based on observed data, without considering data imputation. For table analyses based on the safety analysis set, all subjects receiving at least one treatment with the study device will be included in the analysis. However, for listing analyses, all subjects with safety evaluations will be included, even if they did not receive any trial treatment.

Unless otherwise specified, baseline data shall be defined as the last valid measurement taken before the implant procedure.

When multiple observation data points exist for the same examination at the same follow-up time point, the observation closest in time to the scheduled visit date will be designated as the primary analysis record for the relevant statistical analysis.

Statistical analysis was performed using SAS 9.4[®] software. Subject information and safety databases were exported and stored in SAS XPORT format.

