4.1.1. Full Analysis Set (FAS)

Full analysis set (FAS): According to the basic principles of Intention to Treat (ITT), FAS refers to the set of subjects that comply with the ITT principles. It includes:

- a) Subjects who have been treated with the investigational device, achieved the immediate operation success, and have at least one observation data of primary endpoints after baseline;

- b) Subjects who have received treatment with the investigational device, but have failed in the implantation because of the device itself, regardless of whether there is a study device in the body.

If the implantation is abandoned due to other clinical reasons and there is no investigational device in the body, such subject will not be included in the FAS. The definition of receiving the investigational device treatment is that if any part of the device, including the occluder itself and its delivery device, contact with human body through vascular approach, it can be considered as receiving the device treatment. FAS will be the main data set for baseline data analysis, primary safety, and efficacy evaluation.

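### The SAP names no analysis set for the immediate operation success rate; the default set, the FAS, depends for entry on that same outcome, so the rate can be biased upward.

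*SAP*

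**What the plan says.** The protocol Synopsis classes the endpoint as efficacy: "Secondary efficacy endpoint: immediate operation success rate". It is the only secondary efficacy endpoint. Its definition (both discs seated, release without displacement or migration, delivery system withdrawn) does not mention why an attempt failed.

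SAP 5.2 plans frequencies and percentages, states that "no formal statistical inference will be performed", and adds that "the 95% confidence interval for the immediate operation success rate will be calculated using the exact method". It names no analysis set. SAP section 4 says of percentages that "the number of subjects in the specified analysis population will serve as the denominator", so a set has to be specified somewhere.

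The general rules point to the FAS. Protocol 8.9(4): "The efficacy evaluation of the device is mainly based on FAS". SAP 4.1.1: "FAS will be the main data set for baseline data analysis, primary safety, and efficacy evaluation".

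FAS membership in SAP 4.1.1 (the same in protocol 8.9(1)) works as follows:

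- Limb (a) begins "Subjects who have been treated with the investigational device, achieved the immediate operation success" and also asks for at least one primary-endpoint observation after baseline.
- Limb (b) keeps treated subjects whose implantation failed because of the device itself.
- An exclusion sentence removes others: "If the implantation is abandoned due to other clinical reasons and there is no investigational device in the body".

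The same section counts a subject as having received device treatment once any part of the occluder or delivery device has contacted the body by the vascular route.

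**The concern.** A success rate should be taken over everyone in whom the procedure was attempted. If the FAS is used here, a success enters because it succeeded, while a failure enters only if it is put down to the device. The denominator is then partly chosen by the outcome being measured.

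The documents expect failures of other kinds. Protocol 13.1.4.1 provides for giving up the intervention when intraoperative heart block does not recover. Protocol 7.1.7.1 traces displacement to anatomy, measurement and operator technique. Protocol 8.2.1 expects learning curves and differences between centres. A technical success rate should capture such events.

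Whether a failed attempt counts would rest on attributing it to the device or to something else. The trial is single-arm, and neither document gives criteria or an independent adjudicator for that judgement. The 360-day report supports the marketing application (SAP 3.1), and its readers would take the figure as technical success among all attempts.

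**Working it through.** **The plan's own figures.** Neither document gives a target, performance goal or expected failure count for this endpoint. The only design figure is the sample size for the co-primary endpoints: [1.96·√(0.94·0.06) + 0.8416·√(0.99·0.01)]² / 0.05² = 120.65, so 121, as in protocol 8.2.1; 121 × 1.2 = 145.2, so 146. This supplies N = 146 and does not otherwise bear on the point. SAP 3.1 plans 142.

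**Where each kind of attempt goes.**

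| Attempt in a treated subject | Place in the FAS | Under the endpoint definition |
|---|---|---|
| Success with a primary-endpoint observation after baseline | in, limb (a) | success |
| Success without such an observation | not in limb (a) | success |
| Failure caused by the device | in, limb (b) | failure |
| Failure for another clinical reason, nothing left in the body | excluded | failure |
| Failure for another reason, device left in the body | not assigned | failure |

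No other set is assigned to fill the gap. The per-protocol set is a subset of the FAS. The safety set takes treated subjects whether or not they succeeded, but SAP 4.1.2 gives it to the other safety analyses.

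**Size.** Let N be subjects treated, m device-caused failures, and k other failures left out of the FAS.

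- FAS rate = (N − m − k)/(N − k)
- All-treated rate = (N − m − k)/N
- Difference = FAS rate × k/N

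Each omitted failure therefore adds at most 1/146 = 0.68 points (1/142 = 0.70 points at the SAP's N). The counts m and k below are assumptions. Where intervals are shown, they are Clopper-Pearson 95%.

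| m | k | FAS rate | All-treated rate | Difference (points) |
|---|---|---|---|---|
| 1 | 0 | 145/146 = 99.32% | 145/146 = 99.32% | 0 |
| 1 | 1 | 144/145 = 99.31% | 144/146 = 98.63% | 0.68 |
| 1 | 3 | 142/143 = 99.30% (96.17 to 99.98) | 142/146 = 97.26% (93.13 to 99.25) | 2.04 |
| 1 | 5 | 140/141 = 99.29% (96.11 to 99.98) | 140/146 = 95.89% (91.27 to 98.48) | 3.40 |
| 1 | 10 | 135/136 = 99.26% | 135/146 = 92.47% | 6.80 |
| 0 | 3 | 143/143 = 100% | 143/146 = 97.95% | 2.05 |
| 0 | 5 | 141/141 = 100% | 141/146 = 96.58% | 3.42 |

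With m = 0 the FAS rate is 100% for any k, provided that all k failures are left out. With m = 0 and k = 6 the FAS gives 140/140, interval about 97.4% to 100%, while the all-treated rate is 140/146 = 95.9% (91.3% to 98.5%). The first interval then excludes the second rate.

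**Offset.** Limb (a) also drops successes with no observation after baseline, which lowers the FAS rate. With m = 1 and k = 0, losing one such subject gives 144/145 = 99.310% against 145/146 = 99.315%; losing three gives 142/143 = 99.301%. That is 0.005 to 0.014 points, far too little to cancel the upward effect.

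**The case against.** **The FAS is inferred.** SAP 5.1 assigns the FAS and per-protocol set by name to the primary endpoints only. The sentence in 4.1.1 on primary safety and efficacy could be read as covering primary efficacy alone, and protocol 8.9(4) says only that efficacy rests mainly on the FAS. This stands in part. A reader might infer that the SAP states the rate is computed in the FAS; it does not. The FAS is the likelier reading of an efficacy endpoint, and on the other reading no denominator is defined. Both readings need the same correction.

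**The set does not guarantee success.** A reader might infer that the rate is inflated by construction or fixed near 100%. The documents do not support that: device-caused failures stay in and count, and there is no bias if no other failure occurs. Nor does the text drop every non-device failure. The exclusion covers only attempts with nothing left in the body, and an analyst who follows the stated intention-to-treat basis could count the unassigned ones as failures.

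**Nothing is decided on this endpoint.** This stands. It has no performance goal, and qualification rests on the co-primary endpoints (protocol 8.5, SAP 5.1.2). Excluded attempts with safety data also remain in the safety set, so the all-treated rate could largely be recovered. That limits the consequence, but the planned figure would still be the restricted one.

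**Conclusion.** The point holds in a limited form. SAP 5.2 leaves the analysis set open, and the general rule leads to a set whose membership depends on the outcome. If at least one non-device failure is left out, the rate is too high by about 0.7 points per such failure at N = 146, and 2.0 points in the example with one device-caused and three other failures. The direction follows from the text. The size rests on assumed failure counts, since the documents give none, and on the reading that the FAS applies.

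The interval would still be a valid description of a cause-restricted rate, but that is not the endpoint as defined. A reader might go on to infer that the trial's conclusion is affected, or that the FAS is unsuitable for the co-primary endpoints. The first does not follow, because the endpoint is descriptive. The second is a separate question on which this point takes no position. The change is worth making, but the trial's pass/fail result does not depend on it.

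**What to change.** In SAP 5.2:

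- State that the denominator is all subjects who received device treatment under the plan's own definition in 4.1.1, that is, vascular contact with any part of the occluder or its delivery device.
- Count every attempt that does not meet the success definition as a failure, whatever its cause.
- List the failed attempts by cause, and show which of them lie outside the FAS.

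For this endpoint, that removes the need to decide whether a failure was due to the device, and it settles the unassigned cases.

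The cost is a short addition to the SAP and a small listing, with no new data. The reported rate may be lower. If protocol 8.7.4(10) is edited to match, protocol 12.2 requires ethics committee approval before the change takes effect.

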6. SAFETY ANALYSIS

Safety evaluation endpoints include adverse events, laboratory test results, electrocardiogram (ECG) results, imaging assessments (chest X-ray and echocardiography), and vital signs. All safety endpoints will be analyzed descriptively based on the SS.

6.1. Adverse Events

Adverse events that may occur in this study include: (1) common complications; (2) expected or unexpected serious adverse events (SAEs); and (3) expected or unexpected adverse events (AEs). All adverse events will be coded using the Medical Dictionary for Regulatory Activities (MedDRA), Version 20.0.

All treatment-emergent adverse events (TEAEs) occurring during the study period will be

included in the analysis, including events occurring intraoperatively and postoperatively. The following categories of adverse events will be summarized by the number and percentage of subjects: TEAEs, serious adverse events (SAEs), device-related adverse events, device-related serious adverse events, procedure-related adverse events, procedure-related serious adverse events, adverse events leading to study discontinuation, and adverse events resulting in death.

6.1.1. Treatment-emergent Adverse Events

All TEAEs will be summarized by System Organ Class (SOC) and Preferred Term (PT), and the incidence will be presented accordingly. At each level of summarization, if a subject experiences one or more adverse events within a given category, the subject will be counted only once and will not be counted repeatedly. All percentages will be calculated using the total number of subjects in the SS as the denominator.

If the relationship of an adverse event to the investigational device or the procedure is unclear, it will be classified as related for analysis purposes. In the categorization of relationship to the investigational device or procedure, events assessed as possibly related, probably related, or definitely related will be grouped as related, whereas events assessed as not related or unlikely related will be grouped as unrelated.

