7.1.7.2 Other safety endpoints

- (1) Rate of device-related AEs

Evaluation time: During the trial

Definition of device-related AE: refers to AE that is determined by the investigator to be related, possibly related, unlikely related to the device or the correlation between AE and device is unable to be judge. However, normal postoperative stress reactions, such as fever and constipation, should be distinguished, and those judged by investigators as normal postoperative stress reactions do not need to be recorded in adverse events.

- (2) Rate of SAEs

Evaluation time: During the trial

Serious adverse events refer to events that cause death or serious deterioration of health, including fatal

diseases or injuries, permanent defects of body structure or body functions, hospitalization or prolonged hospital stay, and medical or surgical intervention to avoid causing permanent defects to the body structure or body functions; or that cause fetal distress, fetal death or congenital abnormalities, congenital defects, in the process of the clinical study.

7.1.8 Device deficiency and corresponding evaluation, recording and analyzing method and time:

[figure not shown]
Rate of device deficiencies

Evaluation time: During the operation

Definition of device deficiency: refers to the deficiency of the investigational device which presents in the trial process, such as label error, plastic thread damage, ineffective fastening or release of the locking piece, displacement of shunt blocking membrane, etc.

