13.1.3 Determination of the relationship between AE and test product and operation

The subject should evaluate the correlation between the AE and test device or operation, and classify according to the following criteria:

(1) Correlation with test device

- 1) Definitely relevant: The reaction conforms to the known reaction type of the suspected product.
- 2) Possibly related: The reaction conforms to the known reaction type of the suspected product; The patient's clinical status or other treatment methods may also produce this reaction.
- 3) Possibly irrelevant: The reaction does not quite conform to the known reaction type of the suspected product; The patient's clinical status or other treatment methods may produce this reaction.
- 4) Definitely irrelevant: The reaction does not conform to the known reaction type of the suspected product; The patient's clinical status or other treatment methods may produce this reaction, and the disease state may be improved or the reaction may be eliminated by withdrawal of other treatment methods, and present again upon the repeated use of other treatment methods.
- 5) Unable to judge: The reaction is similar to the known reaction type of the suspected product, and other treatments used at the same time may also cause the same reaction.

(2) Correlation with operation

- 1) Definitely relevant: The reaction conforms to the known reaction type of the operation.
- 2) Possibly related: The reaction conforms to the known reaction type of the operation; The patient's clinical status or other treatment methods may also produce this reaction.
- 3) Possibly irrelevant: The reaction does not quite conform to the known reaction type of the operation; The patient's clinical status or other treatment methods may produce this reaction.
- 4) Definitely irrelevant: The reaction does not conform to the known reaction type of the operation; The patient's clinical status or other treatment methods may produce this reaction, and the disease state may be improved or the reaction may be eliminated by withdrawal of other treatment methods, and present again upon the repeated use of other treatment methods.
- 5) Unable to judge: The reaction is similar to the known reaction type of the operation, and other treatments used at the same time may also cause the same reaction.

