3.2.3. Other Safety Endpoints

- Incidence of device-related Adverse Events (AE);
- Incidence of Serious Adverse Events (SAE);
- Lab test indicator;
- 12-lead ECG indicator;
- Imaging examination (Chest X-ray and Echocardiography)
- Vital signs indicator.

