4.1.2. Safety Set (SS)

Safety Set will include all subjects who have been treated with the device at least once and have safety evaluation data. SS will be the main data set for other safety analysis excepting the primary safety endpoints.

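### The SAP classes unlikely-related adverse events as unrelated, while the protocol counts them as device-related for the same endpoint

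*SAP*

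**What the plan says.** Protocol 7.1.7.2 lists the rate of device-related AEs among the other safety endpoints. Its definition "refers to AE that is determined by the investigator to be related, possibly related, unlikely related to the device or the correlation" cannot be judged. Four judgements therefore make an event device-related: related, possibly related, unlikely related, and not assessable.

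SAP 3.2.3 carries the same endpoint, "Incidence of device-related Adverse Events (AE"), and does not redefine it. The grouping comes in SAP 6.1.1. Possibly, probably and definitely related events form the related group, "whereas events assessed as not related or unlikely related will be grouped as unrelated". Where the relationship is unclear, "it will be classified as related for analysis purposes".

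Protocol 13.1.3 sets the scale for assessing each event. Its five categories are definitely relevant, possibly related, possibly irrelevant, definitely irrelevant and unable to judge. Two of them matter here: "Possibly irrelevant: The reaction does not quite conform to the known reaction type of the suspected product" and "Unable to judge: The reaction is similar to the known reaction type of the suspected product". The label *unlikely related* is not on that scale, and the SAP's *probably related* appears in neither protocol section.

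**The concern.** One label, *unlikely related*, falls on opposite sides of the line in the two documents, for one named endpoint. The protocol's definition is deliberately wide and includes events of doubtful causality. The SAP narrows it without comment. Protocol 8.8 expects reporting to follow an analysis plan that accords with the protocol, and sends other cases to a discussion with the principal investigator and experts; the SAP mentions no such decision.

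At stake is whether the reported rate is the endpoint that the protocol defined. The trial has no concurrent control, and SAP 3.1 says the 360-day analysis will support the marketing application, so a causality-based rate will be read at face value. A second difficulty is practical. Events recorded on the 13.1.3 scale do not carry the SAP's labels, so a programmer following SAP 6.1.1 literally has no instruction for *possibly irrelevant*.

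**Working it through.** The documents state no expected device-related AE rate, so there is no figure to reproduce. The check is one of classification.

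**Step 1: put the two rules on the recorded scale.** Three read-across assumptions are needed, none of them stated in the documents:

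- A1: *possibly irrelevant* (13.1.3) is the counterpart of *unlikely related* (7.1.7.2 and SAP 6.1.1).
- A2: *unclear* (SAP 6.1.1) means *unable to judge* (13.1.3) and nothing else.
- A3: *probably related* (SAP 6.1.1) falls under the protocol's *related*.

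| Category in protocol 13.1.3 | Protocol 7.1.7.2 | SAP 6.1.1 |
|---|---|---|
| Definitely relevant | device-related | related |
| Possibly related | device-related | related |
| Possibly irrelevant (A1) | device-related | unrelated |
| Definitely irrelevant | not device-related | unrelated |
| Unable to judge (A2) | device-related | related |

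Only one row differs.

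**Step 2: move from events to subjects.** A subject counts once if any event qualifies. Five categories give 2^5 = 32 possible profiles for a subject. Classifying all 32 under both rules, the SAP counts more in 0, the same in 30, and fewer in 2. Those two are subjects with *possibly irrelevant* events only, and subjects with *possibly irrelevant* and *definitely irrelevant* events only.

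**Step 3: size.** Let k be the number of subjects in those two profiles and N the Safety Set size. For the same subjects and denominator,

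protocol rate − SAP rate = k/N.

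Neither k nor N is given. Taking N as planned enrolment is an assumption: 142 (SAP 3.1) or 146 (protocol 8.2.1).

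| k | N = 142 | N = 146 |
|---|---|---|
| 0 | 0 | 0 |
| 1 | 1/142 = 0.70 points | 1/146 = 0.68 points |
| 2 | 2/142 = 1.41 points | 2/146 = 1.37 points |
| 5 | 5/142 = 3.52 points | 5/146 = 3.42 points |

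The values of k only illustrate the scale; they are not estimates.

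**Step 4: relax the assumptions.**

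- Without A1, no event on the recorded scale is literally *unlikely related*, and neither document says where *possibly irrelevant* goes.
- Without A2, if *unclear* also covers missing assessments, a subject whose only events lack an assessment would count under the SAP but is not named in 7.1.7.2. The SAP count could then be higher.
- Without A3, if *probably related* were used and read as outside the protocol's list, there are 2^6 = 64 profiles. In 2 of them (*probably related* alone, or with *definitely irrelevant*) the SAP counts a subject whom the protocol does not.

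**The case against.** The best case against the point is about weight. This is an other safety endpoint with no hypothesis or threshold, and SAP 6 makes all safety analysis descriptive. SAP 6.1 and 6.1.1 tabulate all treatment-emergent AEs and all SAEs whatever their causality, so no event disappears from the report. The 94% and 6% co-primary decision does not use relatedness. The number k is unknown and may be zero. All of this stands, and it limits the consequence.

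A reader might go further and infer that the SAP rate can only be equal to or lower than the protocol rate. The documents do not support that without conditions. It needs all three assumptions A1 to A3, and Step 4 shows that the direction can reverse for some subjects if A2 or A3 fails.

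A reader might also look to the denominator, since the Safety Set is worded differently: protocol 8.9 has it "including all subjects who have been treated with the device at least once", while SAP 4.1.2 requires "all subjects who have been treated with the device at least once and have safety evaluation data". This is a side issue. SAP 4 says that Safety Set tables include every subject treated at least once, which largely removes the difference. The comparison above holds the denominator fixed.

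None of these arguments reconciles the two definitions. The shared label *unlikely related* is classified in opposite ways on the face of the text, and no other section resolves it.

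**Conclusion.** The point holds as a conflict of definition: SAP 6.1.1 would compute a named safety endpoint by a rule that contradicts protocol 7.1.7.2, without a stated reason. That conclusion needs no assumption.

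The direction and size are conditional. Under A1 to A3, with the same subjects and denominator, the SAP numerator is equal or lower, by k subjects. Each is about 0.7 percentage points if the Safety Set is taken as 142 or 146. Nothing in the documents shows that k is above zero, so it cannot be said that the reported rate will be understated. The matter should be corrected before analysis because the correction is cheap and the endpoint is pre-specified, but it does not bear on the trial's success criterion.

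**What to change.** In SAP 6.1.1, for device-related AEs, replace the present grouping with one mapping of the five categories in protocol 13.1.3, following 7.1.7.2:

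- **Device-related:** definitely relevant, possibly related, possibly irrelevant (once the sponsor confirms that it is the counterpart of *unlikely related*), and unable to judge.
- **Unrelated:** definitely irrelevant.

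State also whether *unclear* covers missing causality assessments or only *unable to judge*.

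Alternatively, if the sponsor prefers the narrower definition, amend protocol 7.1.7.2 with a stated reason so that both documents agree.

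The first route costs a change of SAP wording and uses causality assessments that the protocol already requires. Its downside for the sponsor is a possibly higher reported device-related AE rate. The second is a protocol change and needs ethics committee approval before it takes effect (protocol 12.2).
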